6.1.2.2 DURATION OF RESPONSE

The Duration of Response (DOR) is defined as the interval from the first documentation of CR or PR to the earlier of the first documentation of disease progression or death from any cause.

The DOR rate will be compared between treatment groups at the 5%, two-sided statistical significance level using stratified log-rank test. The median DOR will be estimated by Kaplan-Meier method, The hazard ratio (HR) with 2-sided 95% confidence interval will be estimated using stratified Cox regression model. The DOR analysis will be performed for responders only (CR/PR) in the ITT population.

6.1.2.3 TIME TO TREATMENT RESPONSE

The Time to Treatment Response (TTR) is defined as the interval from the date of randomization to the first documentation of CR or PR. In this analysis, subjects who never reached response will be censored at the time of last assessment.

This variable will be analyzed using stratified log-rank test and median TTR will be estimated via Kaplan-Meier methodology. The HR with 95% CI will be analyzed using a stratified Cox regression model.

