6.1 PRIMARY EFFICACY OUTCOME

6.1.1 PRIMARY OBJECTIVE: OVERALL RESPONSE RATE

ORR is defined as the proportion of patients with a best overall response of partial response (PR) or complete response (CR). Patients who do not have a tumor response assessment for any reason will be considered non-responders and will be included in the denominator when calculating the ORR. For the ITT analysis, for each treatment group, the number of patients achieving a response will be divided by the total of patients in the ITT population to yield the proportion responding.

The primary efficacy variable (i.e. ORR) will be analyzed in the ITT population first and then will also be analyzed for the Treated Population.

The ORR will be compared between treatment groups by the CMH Test controlling for the randomization strata. Testing of ORR will be at the 5%, 2-sided statistical significance level.

ORR will also be analyzed based on Per Protocol patients. Additional sensitivity analyses will also be performed as appropriate.

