6.2 ANALYSIS METHODS: DOR AND PFS

The date of definitive progression will be the timepoint at which progression is first identified and confirmed by the independent radiographic committee. Death following the discontinuation of study drug will be considered as an event for the DOR and PFS calculation. Data will be censored on the date of the last tumor assessment (including assessments with a Not Evaluable (NE) outcome) for patients who:

- Start alternative anti-tumor therapy prior to disease progression
- Do not have disease progression within 30 days after discontinuation of study drug(s)

TG Therapeutics, Inc. UTX-IB-301 SAP

secondary outcomes will be tested:

If the primary efficacy analysis of ORR is statistically significant for the ITT population, the following

- Complete response rate
- Duration of response
- · Time to response

For each of these outcomes, ublituximab + ibrutinib will be compared to ibrutinib. The Hochberg approach will be used to control the type I error rate. The null hypotheses state that the secondary outcomes do not differ between ublituximab + ibrutinib and ibrutinib. The three p-values associated with these three secondary outcomes are denoted p_1 , p_2 , and p_3 . The ordered p-values, from largest to smallest, are denoted $p_{(1)} \ge p_{(2)} \ge p_{(3)}$. Specifically:

- If $p_{(1)}$ is less than 0.05, all three null hypotheses will be rejected.
- Otherwise, if $p_{(2)}$ is less than 0.025, the null hypotheses associated with $p_{(2)}$ and $p_{(3)}$ will be rejected.
- Otherwise, if $p_{(3)}$ is less than 0.0167, the null hypothesis associated with $p_{(3)}$ will be rejected.

If the primary efficacy analysis of ORR is not statistically significant, the secondary efficacy variable defined above will not be formally conducted.

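### TTR censors patients who progressed or died without responding, so its Kaplan-Meier curve and median overstate response, and its test can diverge from the ORR that gates it

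*SAP*

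**What the plan says.** SAP 6.1.2.3 measures TTR from randomization to the first CR or PR. Its rule for everyone else is one sentence: "In this analysis, subjects who never reached response will be censored at the time of last assessment". On method it says: "This variable will be analyzed using stratified log-rank test and median TTR will be estimated via Kaplan-Meier methodology". The hazard ratio comes from a stratified Cox model.

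Nothing elsewhere narrows the rule. Protocol 11.10.2.1.3 is silent on non-responders, SAP Table 3 covers PFS, and SAP 6.2 covers DOR and PFS.

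Two other places bear on it:

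- **Primary ORR (SAP 6.1.1).** "Patients who do not have a tumor response assessment for any reason will be considered non-responders", and they stay in the denominator.
- **Best overall response (protocol 10.4).** It is read from the start of treatment only until progression.

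The multiplicity rule (6.5 in the SAP contents, printed after the 6.2 text) begins "If the primary efficacy analysis of ORR is statistically significant for the ITT population, the following" and then lists CR rate, DOR and TTR. It continues: "The Hochberg approach will be used to control the type I error rate".

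**The concern.** Censoring suits a patient with stable disease who is still being scanned, because a response may yet come. It does not suit a patient who has progressed or died, because under protocol 10.4 the chance of a later response is zero. Kaplan-Meier nevertheless gives each censored patient the response experience of those still at risk. The resulting curve estimates response in a setting where nobody fails first, which is not the share of randomized patients who respond by a given week.

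The primary ORR keeps the same patients as failures, so the two endpoints answer different questions while one gates the other. The TTR p-value also reaches beyond TTR. If it is pushed to 0.05 or above, CR rate and DOR can no longer be claimed at 0.05 and must meet the 0.025 step. The trial is open label and only one arm receives infusions, so unequal exits are plausible.

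**Working it through.** **The plan's own figure.** Hochberg steps for three outcomes at 0.05 are 0.05/1 = 0.05, 0.05/2 = 0.025 and 0.05/3 = 0.0167. The SAP thresholds reproduce. No expected response, progression or dropout rate can be read in the documents, so every rate below is an assumption.

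**Worked example.** About 120 patients at 1:1 gives 60 per arm (SAP 3.6). Cycles of 28 days put the first scans at weeks 8, 16 and 24. *Exits* are patients who progress, die or leave without a response.

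- Arm A: 24, 16 and 8 responses, 48/60 = 80%, with one exit after week 8 and one after week 16.
- Arm B: 18, 12 and 6 responses, 36/60 = 60%, with six exits after week 8 and six after week 16 (12/60 = 20%).
- ORR chi-square p = 0.017, so the gate is passed.

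The log-rank test is unstratified. At each scan, with n_A and n_B at risk, n in total and d responses, E = d·n_A/n and V = d·(n_A/n)·(n_B/n)·(n−d)/(n−1). HR = exp((O−E)/V), and HR > 1 means faster response in Arm A.

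*SAP rule.* At risk: A 60, 35, 18; B 60, 36, 18.
- E = 42×60/120 + 28×35/71 + 14×18/36 = 21.00 + 13.80 + 7.00 = 41.80
- V = 6.88 + 4.30 + 2.20 = 13.38
- HR = exp((48 − 41.80)/13.38) = 1.59, p = 0.090

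*Exits kept in the risk set.* At risk: A 60, 36, 20; B 60, 42, 30.
- E = 21.00 + 28×36/78 + 14×20/50 = 21.00 + 12.92 + 5.60 = 39.52
- V = 6.88 + 4.52 + 2.47 = 13.87
- HR = exp((48 − 39.52)/13.87) = 1.84, p = 0.023

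*Week-24 Kaplan-Meier response in Arm B.* 1 − (42/60)(24/36)(12/18) = 68.9%, against an actual 60%. In Arm A it is 1 − (36/60)(19/35)(10/18) = 81.9%, against 80%.

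Varying only the Arm B exits (2 in Arm A throughout; with exits kept, HR 1.84 and p = 0.023 in every row):

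| Arm B exits | SAP-rule HR | p | Week-24 KM in B (actual 60%) |
|---|---|---|---|
| 2 (3%) | 1.88 | 0.020 | 61.1% |
| 6 (10%) | 1.77 | 0.036 | 63.7% |
| 12 (20%) | 1.59 | 0.090 | 68.9% |
| 22 (37%) | 1.22 | 0.48 | 89.3% |

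**Simulation.** 60 per arm, scans at weeks 8, 16, 24, 36 and 48. Per-scan response chances are .50/.40/.25/.15/.10 in Arm A and .35/.35/.25/.15/.10 in Arm B. Arm A exits total about 4%. The test is a single two-sided 5% test, before the ORR gate and Hochberg.

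| Exits, B v A | TTR rejects, SAP rule | TTR rejects, exits kept |
|---|---|---|
| 10% v 4% | 27% | 33% |
| 19% v 4% | 28% | 52% |
| 36% v 4% | 29% | 81% |

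A repeat of the first row gave 28% and 35%. The SAP-rule column barely moves because the hazard contrast among patients still at risk is fixed. The other column rises because Arm B's exits lower its response rate.

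**Can the endpoints point in opposite directions?** In one constructed case ORR is 46/60 v 34/60 (p = 0.020, gate passed) with exits of 4 v 26. The SAP rule gives HR 0.48 against Arm A (p = 0.021); with exits kept, HR is 1.42 (p = 0.19). That needs 26/60 = 43% of one arm to exit.

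**The case against.** The strongest defence is that the log-rank test under this censoring is a valid test of the cause-specific hazard of response. That stands. The 29% against 81% contrast compares two questions and does not show a wrong test size. Keeping exits in the risk set also moves TTR closer to a second look at ORR.

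The exit rates are a further limit. SAP 6.1.2.5 expects most patients in both arms not to have progressed at the primary ORR analysis. Protocol 6.1 and 6.4 keep patients who stop treatment under follow-up for progression, so stopping treatment is not in itself an exit. This stands too and makes the first two simulation rows more relevant than the third.

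Four stronger readings are tempting, and the documents do not support them:

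- *Failed patients are treated as future responders.* Censoring assumes only that they share the later response chance of patients still at risk. That is wrong for patients who progressed or died, but it is not an assumption that they respond.
- *TTR could support a formal claim for the arm with the lower ORR.* TTR is tested only after ORR succeeds in ITT. In a simulation where Arm A responds faster but loses more patients (ORR 64% v 73%), TTR alone favours Arm A in about 30% of trials, yet ORR is also significant in about 1 trial in 1,000.
- *Unscanned ITT patients leave the risk set at once.* SAP 6.1.2.3 does not say what the last assessment is for them. This is a gap, not a stated rule.
- *Tied response times distort the hazard ratio.* The SAP names no tie method, so this is missing detail, and it does not affect the log-rank test.

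None of this rescues the Kaplan-Meier curve or median as a description of randomized patients.

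**Conclusion.** The point holds in a limited form. Whenever patients progress or die before responding, the planned curve and median overstate response in the randomized population. The formal comparison then measures something other than what the gating ORR measures.

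On the assumed rates the effect is small at about 10% v 4% exits, moderate at 19% v 4%, and large only with heavy, unequal exits. Results that contradict ORR are a reporting risk and almost never a formal claim.

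These sizes rest on assumed response and exit rates, an unstratified test, follow-up to week 24 or 48 (SAP 3.5.1 guarantees only 16 weeks), and counting every exit as a non-responder. The change should be made because TTR is formally tested and the correction is cheap. It is not a threat to the primary analysis.

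**What to change.** Amend SAP 6.1.2.3 before database lock:

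1. Treat progression and death without a prior response as competing events, and new anticancer therapy likewise. Keep these patients in the risk set as non-responders to the data cut-off.
2. Report the cumulative incidence of response by arm, compared with a stratified Gray test, in place of the Kaplan-Meier median. An equivalent device is to censor these patients at the maximum follow-up time.
3. Censor at last assessment only patients without a response who have had no such event. Whether loss to follow-up should also count as failure is a trade-off; state the choice.
4. Handle ITT patients with no post-baseline assessment consistently with SAP 6.1.1.
5. Name the tie method for any hazard ratio.

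The cost is SAP wording and a standard procedure, with no new data. The hazard ratio becomes a subdistribution hazard ratio and needs a line of explanation; the cause-specific one can stay as supportive. A simpler alternative is to describe TTR in responders only and take it out of the Hochberg family.

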6.1.2.4 MINIMAL RESIDUAL DISEASE NEGATIVITY RATE

MRD negativity rate is defined as the proportion of patients in the Treated Population who are MRD negative, excluding any patients who remain on study treatment at the time of the analysis and have a Cycle 1/Day 1 start date less than 6 months from the time of the analyses. For the sake of clarity, the MRD negative analysis will exclude those patients that are too early to evaluate because MRD negativity is only tested for patients on study \geq 6 months. Patients who drop off study for any reason prior to their 6 month visit and do not have an MRD assessment will be included in the analysis and considered non-responders.

For each treatment group, the number of patients achieving MRD negativity will be divided by the total number of eligible patients (see above paragraph) to yield the proportion responding. The MRD negativity rate will be compared between treatment groups at the 5%, two-sided statistical significance level using the same methodology described in Section 6.1.1.

6.1.2.5 PROGRESSION-FREE SURVIVAL

Progression-free survival is defined as the time from the date of randomization until the date of first documentation of definitive disease progression or date of death from any cause, whichever occurs first. Patients who die without a reported prior progression will be considered to have progressed on the day of their death. Patients who did not progress or are lost to follow-up will be censored at the day of their last tumor response assessment. If no baseline or post-baseline assessment is available, the patient will be censored at the date of randomization. If death or PD occurs after 2 or more consecutive missing tumor response assessments, censoring will occur at the date of the last response assessment prior to the missed assessments. The use of a new anticancer therapy prior to

the occurrence of PD will result in censoring at the date of last tumor response assessment prior to initiation of new therapy.

This variable will be analyzed using stratified log-rank test, and median PFS will be estimated via Kaplan-Meier methodology. PFS may not be formally analyzed at the time when the planned formal ORR analysis is conducted with approximately 120 patients who have had the opportunity to provide two efficacy assessments as it is expected that the majority of the patients from both treatment arms will not have progressed by the time of the primary ORR analysis (PFS may not be reliably estimated due to high censoring). Following the primary analysis of ORR, PFS may be analyzed at a later date. PFS will be analyzed using a stratified Cox regression model with treatment effect and stratification effect to estimate HR and 95% CI.

Censoring rules for PFS are summarized in Table 3.

TABLE 3: CENSORING RULES FOR PFS

Situation	Date of Progression or Censor	Censored/ Progressed
No baseline radiological tumor assessments	Randomization date	Censored
No post-baseline tumor assessments and no death reported before data cut-off	Randomization date	Censored
Disease progression	Date of progression	Progressed
No disease progression	Date of last tumor assessment	Censored
Treatment discontinuation for toxicity or other reasons with no disease progression per IRC	Date of last tumor assessment	Censored
Patient lost to follow-up without disease progression	Date of last tumor assessment	Censored
Death before first tumor assessment	Date of death	Progressed
Death between adequate tumor assessments	Date of death	Progressed
Death or disease progression after ≥ 2 missed tumor assessments	Date of last tumor assessment before missed assessments or randomization date if no other tumor assessment in between	Censored
Withdrawal due to symptomatic deterioration without further tumor assessments	Date of last tumor assessment before discontinuation	Censored
Patient use of any anti-cancer therapy and/or surgery for curative intent.	Date of last tumor assessment prior to therapy or surgery, whichever occurs first	Censored
Note: Progression-free survival = date of even	t / censor – randomization date + 1	

Once the progression and survival dates are derived, PFS will be calculated as follows for patients with a PFS event:

PFS (days) = date of PD or death due to any case – randomization date + 1

(with censoring indicator = event)

For those patients who are censored for a PFS event:

[figure not shown]
PFS (days) = date of censoring – randomization date + 1

(with censoring indicator = censored)

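### The SAP's sentence censoring unscanned patients at randomization makes no exception for deaths; Table 3 corrects this for the commonest case but contradicts itself in two rarer ones

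*SAP*

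**What the plan says.** SAP 6.1.2.5 runs PFS from randomization to the "date of first documentation of definitive disease progression or date of death from any cause, whichever occurs first". It then gives two rules that bear on a patient who dies without having been scanned:

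- "Patients who die without a reported prior progression will be considered to have progressed on the day of their death". No condition on scans is attached.
- "If no baseline or post-baseline assessment is available, the patient will be censored at the date of randomization". No condition on vital status is attached.

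Protocol 11.10.2.1.6 has the same two sentences and no censoring table.

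Four rows of SAP Table 3 matter here:

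- "No baseline radiological tumor assessments": censored at the randomization date, with nothing said about death.
- "No post-baseline tumor assessments and no death reported before data cut-off": censored at the randomization date.
- "Death before first tumor assessment": event on the date of death.
- "Death or disease progression after ≥ 2 missed tumor assessments": censored, at the "Date of last tumor assessment before missed assessments or randomization date if no other tumor assessment in between".

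The prose version of the last rule requires the missed assessments to be *consecutive*; the table row does not. SAP 6.2 adds that a death after stopping study drug is an event for PFS. In the same paragraph it censors patients without progression within 30 days of stopping. Neither document says which rule wins when two apply.

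**The concern.** PFS includes death from any cause, and a death needs no scan to be observed. Censoring a patient who died on day 1 removes that patient from every risk set and leaves no trace in the PFS estimate. Deaths before the first scan are also where early harm from an added drug would appear, so such censoring would be informative and would favour the arm with more early deaths. The study is open label (SAP 3.6), so an order of precedence chosen after the deaths are known would be hard to defend. The SAP plans a stratified log-rank test and a Cox hazard ratio for PFS, so the choice reaches a reported estimate.

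**Working it through.** The documents state no PFS event count, hazard ratio or power, so there is no figure of the plan's own to reproduce. The check applies each rule to each kind of early death, followed by an illustration of size.

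**Timing.** Scans follow cycles 2 and 4 (SAP 3.1), and a cycle is 28 days (SAP 3.2). They fall due at 2 × 28 = day 56 and 4 × 28 = day 112. With the 7-day window the latest dates are day 63 and day 119.

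**Rule by rule, for a patient who dies without prior progression**

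| Patient | Death sentence | No-assessment sentence | Table 3 |
|---|---|---|---|
| 1. Baseline scan done; dies before the first post-baseline scan is due | Event | Censored, day 1 | Event: the no-post-baseline row requires that no death is reported, and the death-before-first-assessment row applies |
| 2. No baseline scan; dies | Event | Censored, day 1 | Both: censored by the no-baseline row, event by the death-before-first-assessment row |
| 3. Baseline scan done; both first scans missed; dies, for example, at week 18 (18 × 7 = day 126, after day 119) | Event | Censored, day 1 | Both: event by the death-before-first-assessment row, censored at randomization by the missed-assessment row |

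Patient 1 is a conflict of prose with table only. Patients 2 and 3 are conflicts inside the table. If patient 3 stopped treatment at week 3, SAP 6.2 also gives two answers: event by its death sentence, censored by its 30-day bullet.

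**Effect on the curve.** About 120 patients randomized 1:1 (SAP 3.6) is about 60 per arm. With k unscanned early deaths and nothing else happening, early PFS is 1 − k/60 if they are events: 98.3% for k = 1, 95.0% for k = 3 and 91.7% for k = 5. If they are censored at randomization, early PFS stays at 100% and 59, 57 or 55 patients remain at risk.

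**Effect on the hazard ratio (Arm A to Arm B).** All inputs below are assumptions. The two arms otherwise share one event rate, and the early deaths are imposed on Arm A only.

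- *Shorter follow-up.* 60 per arm; 12-month PFS 85%, a monthly hazard of −ln(0.85)/12 = 0.0135; follow-up 6 to 24 months; three deaths at 0.7 to 4.2 months. The median hazard ratio is 1.33 with all three as events and 1.04 with all three censored on day 1. A separate set of simulated trials gave 1.30 and 1.03.
- *Longer follow-up.* Median PFS 36 months; follow-up 12 to 36 months. For three deaths the average hazard ratio is 1.14 as events and 0.99 censored. For one death it is 1.04 and 1.00; for five it is 1.23 and 1.00.

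**Only the conflict inside Table 3.** In the shorter scenario, only deaths after day 112 can meet the missed-assessment row. Day 112 is 112/30.44 = 3.68 months. If deaths are uniform over the window, the share is (4.2 − 3.68)/(4.2 − 0.7) = 0.52/3.5, or about 15%. Censoring only those gives a median hazard ratio of 1.29, so the shift is 1.33 − 1.29 = 0.04. The central 95% of simulated hazard ratios in this scenario runs from about 0.6 to 3.0, far wider than any of these shifts.

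**The case against.** A reader might infer that the plan lets early deaths in general be dropped from PFS, and might take the contrast of about 1.3 with about 1.0 as its consequence. The documents do not support that. Table 3 censors a patient without post-baseline scans only if no death was reported, and gives death before the first assessment its own row as an event. SAP 6.2 also counts death after stopping drug as an event. The full contrast arises only if a programmer follows the prose sentence against the table.

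The prose can also be read in sequence. Deaths are dealt with first, then patients without progression are censored at their last assessment, and the disputed sentence merely supplies a date when there is none. Protocol 11.2 leaves data-handling rules to the SAP, so the protocol's lack of a table adds little. The no-baseline case should be nearly empty, because measurable nodes on CT or MRI are an entry criterion (Protocol 5.1, item 4). Deaths are tabulated in the safety analysis as well.

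Most of this stands, and it limits the point to a clarification with modest consequences. It does not remove the point. The sequential reading is an inference from sentence order. The no-baseline row lacks the no-death condition that the row after it carries. A death after two missed first scans still meets two Table 3 rows with opposite results.

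**Conclusion.** The contradiction is real but narrow. For the commonest early death the table already gives the right answer for an endpoint that includes death, and the prose should be made to agree. Death without a baseline scan, and death after the first two scans were missed, have two answers inside Table 3 and no stated precedence.

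PFS is a secondary endpoint, is outside the Hochberg family (complete response rate, duration of response and time to response), may be analysed only at a later date, and has no formal test in the protocol. ORR is unaffected because unassessed patients count as non-responders. The hazard-ratio figures rest wholly on assumed event rates, follow-up and imbalance: about 1.1 to 1.3 against about 1.0 for three deaths to none if the prose prevails, and a shift of about 0.04 from the table's own conflict in the one scenario examined.

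A reader might also extend the point to duration of response. That is not needed: the analysis is confined to responders, who necessarily have a post-baseline assessment.

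**What to change.** Before database lock, amend the SAP as follows:

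1. Add the condition that no death was reported before data cut-off, as the no-post-baseline row already has it, to the no-assessment sentence in 6.1.2.5 and to the no-baseline row of Table 3.
2. State that a death with no prior post-baseline assessment is an event on the date of death. The missed-assessment rule then applies only to two or more consecutive missed assessments after at least one post-baseline assessment. Put *consecutive* into the table row.
3. Leave the new-anticancer-therapy censoring rule unchanged, and state that it takes precedence over a later death. A blanket rule that every death is an event would silently remove it, and would leave the missed-assessment rule unable to apply to any death.
4. Reconcile the death-after-discontinuation sentence in SAP 6.2 with the 30-day censoring bullet beneath it.

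The cost is a few sentences and one derivation program. The downside is a few more PFS events, possibly less favourable to one arm.

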11.10.2.1.6 PROGRESSION-FREE SURVIVAL

Progression-free survival is defined as the time from the date of randomization until the date of first documentation of definitive disease progression or date of death from any cause, whichever occurs first. Patients who die without a reported prior progression will be considered to have progressed on the day of their death. Patients who did not progress or are lost to follow-up will be censored at the day of their last tumor response assessment. If no baseline or post-baseline assessment is available, the patient will be censored at the date of randomization. If death or PD occurs after 2 or more consecutive missing tumor response assessments, censoring will occur at the date of the last response assessment prior to the missed assessments. The use of a new anticancer therapy prior to the occurrence of PD will result in censoring at the date of last tumor response assessment prior to initiation of new therapy.

This variable will be analyzed via Kaplan-Meier methodology. The median PFS will be estimated for each arm, however no formal hypothesis testing will be conducted.

UTX-IB-301

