3.1 STUDY DESIGN

This study is a fixed-dose, randomized, two-arm Phase 3 trial to assess the efficacy and safety of ublituximab in combination with ibrutinib compared to ibrutinib alone in patients with CLL who have received at least one prior standard treatment regimen and who have at least one high-risk cytogenetic abnormality (17p deletion, 11q deletion, and/or P53 gene mutation).

Following screening, patients meeting the inclusion/exclusion criteria will be randomized in a 1:1 ratio to one of the following treatment regimens:

- Arm A: Ublituximab + ibrutinib
- Arm B: Ibrutinib

Randomization will be stratified according to prior lines of therapy (1 prior vs. 2 or more prior lines of therapy)

All study patients will be evaluated for response after cycles 2, 4, and 6, then every 3 cycles thereafter if patient is on active treatment, or approximately every 3 months thereafter if patient is in follow up. The best clinical response as well as disease progression will be determined by an Independent Review Committee (IRC).

Patients will continue treatment until the occurrence of definitive disease progression, unacceptable toxicity, or withdrawal from the study due to investigator decision or other reasons. Patients who discontinue study treatment for reasons other than disease progression will continue to be followed for progression and/or survival approximately every 3 months.

Upon first assessment scan of the last randomized patient, and site submission of all required efficacy and safety data, the independent DSMB will review the primary and secondary efficacy analyses, and safety data.

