3.6 RANDOMIZATION

In this open label study, approximately 120 patients will be centrally randomized in a 1:1 fashion to one of the two treatment regimens. Investigators will use an interactive web response system (IWRS) which will assign patients to either treatment Arm A (ublituximab plus ibrutinib) or treatment Arm B (ibrutinib alone). Randomization will be stratified by prior lines of therapy (1 prior vs. 2 or more prior lines of therapy).

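### SAP Table 3 omits *consecutive* from the missed-scan censoring rule for PFS, and neither table nor text says that the gap must immediately precede the event; the two should be made one rule before database lock

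*SAP*

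**What the plan says.** The rule is stated three times.

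- **SAP 6.1.2.5, text:** "If death or PD occurs after 2 or more consecutive missing tumor response assessments", the patient is censored at the last response assessment before the missed ones. Protocol 11.10.2.1.6 has the same sentence.
- **SAP 6.1.2.5, Table 3:** the row reads "Death or disease progression after ≥ 2 missed tumor assessments", without *consecutive*. Its date column reads "Date of last tumor assessment before missed assessments or randomization date if no other tumor assessment in between".
- **Link between them:** "Censoring rules for PFS are summarized in Table 3". The SAP does not say which prevails if they differ, and the table gives no order of precedence among its rows.

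Two other rows of Table 3 score events on their own dates: the disease progression row and the row "Death between adequate tumor assessments".

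On schedule and size, the SAP says "All study patients will be evaluated for response after cycles 2, 4, and 6, then every 3 cycles thereafter if patient is on active treatment" (section 3.1) and "approximately 120 patients will be centrally randomized in a 1:1 fashion" (section 3.6). On the role of PFS, the protocol says "The median PFS will be estimated for each arm, however no formal hypothesis testing will be conducted". SAP 6.1.2.5 plans a stratified log-rank test and a Cox hazard ratio, but says that PFS may not be formally analysed with ORR and may be analysed later.

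**The concern.** A missed-assessment rule exists because a long gap just before an event leaves its date uncertain. A gap that evaluable scans have since closed creates no such uncertainty.

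Taken alone, the Table 3 row goes beyond that purpose: any two misses, however far apart, would turn a well-dated progression into a censored observation with an earlier date. The text is narrower, but read literally it also catches an old two-scan gap that later scans have closed.

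Chances to miss two scans accumulate with time on study, so late events would be the ones most often lost. That matters because the SAP allows PFS to be analysed at a later date. SAP section 2 requires the plan to be final before database lock. An ambiguous rule leaves a choice that could otherwise be made after the data are seen.

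**Working it through.** **1. Two patients under each wording** (scans after cycles 2, 4, 6, 9, 12, 15, 18 and so on)

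- *Patient 1* misses the cycle 2 and cycle 12 scans, attends all others, and progresses at cycle 18. Under the text there is no consecutive pair, so this is an event at cycle 18. Under the literal row there are two misses, so it is censored. The date is not determined: before the first miss it is randomization, before the second it is the cycle 9 scan. The disease progression row scores the same patient as an event.
- *Patient 2* misses cycles 4 and 6, attends 9, 12 and 15, and progresses at cycle 18. The ordinary sense of the text makes this an event. A literal reading of *after* censors at cycle 2, although three evaluable scans followed the gap.

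The date column works only for a single unbroken gap. That suggests the consecutive rule was intended, and that the row does not say so.

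**2. Exact calculation for an event at a given scan**

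The plan has no figure of its own to reproduce: it states no PFS event count, median, power or missed-scan rate. Let *k* be the number of scheduled scans before the event and *m* the assumed probability of missing each, independently.

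- Any two missed (literal row): 1 − (1−m)^k − k·m·(1−m)^(k−1)
- A consecutive pair anywhere earlier (literal text): 1 − q_k, where q_0 = q_1 = 1 and q_k = (1−m)·q_(k−1) + m(1−m)·q_(k−2)
- A consecutive pair immediately before the event: m²

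For an event at cycle 24, the earlier scans follow cycles 2, 4, 6, 9, 12, 15, 18 and 21, so k = 8. With m = 0.05, the literal row gives 1 − 0.6634 − 0.2793 = 0.0572, and the immediate rule gives 0.05² = 0.0025.

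| Event at | m (assumed) | Any two missed | Pair anywhere earlier | Pair immediately before |
|---|---|---|---|---|
| Cycle 12 (k = 4) | 5% | 1.4% | 0.7% | 0.25% |
| Cycle 12 (k = 4) | 10% | 5.2% | 2.8% | 1.0% |
| Cycle 24 (k = 8) | 2% | 1.0% | 0.3% | 0.04% |
| Cycle 24 (k = 8) | 5% | 5.7% | 1.7% | 0.25% |
| Cycle 24 (k = 8) | 10% | 18.7% | 6.3% | 1.0% |

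**3. Simulation over a whole follow-up period**

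Assumptions: scans at weeks 8, 16 and 24, then every 12 weeks; independent misses; exponential PFS with median 24 to 48 months; progression found at the first attended scan after it occurs; 120 patients.

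| Follow-up | Scans missed | Progressions censored by literal row | Events per 120 patients |
|---|---|---|---|
| 12 months | 5% | about 0.9% | about 0.2 |
| 24 months | 5% | about 3% | 1 to 1.5 |
| 48 months | 3% | about 3% | – |
| 48 months | 5% | 7 to 9% | 5 to 6 |
| 48 months | 10% | 20 to 24% | 14 to 18 |

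With 5% missed, a rule tied to the gap immediately before the event censors about 0.4 to 0.7% across the three follow-up lengths (about 0.5 event at 48 months). With 10% missed and 48 months it censors about 2.5% (about 2 events). The text read literally, any earlier consecutive pair, censors about 2% and 7 to 8% at 48 months with 5% and 10% missed.

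The simulated figures for the immediate rule exceed m² because a progression that arises during a gap is found only after it, so gaps are over-represented just before detection.

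**The case against.** A reader might infer that Table 3 censors every progression or death after two missed scans, and that real PFS events are therefore removed. The documents do not support that.

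- The table is presented as a summary, directly after a paragraph that contains *consecutive*, and the protocol states the same full rule. Two complete statements agree and the abbreviated one differs.
- The row's date column and the row for death between adequate assessments both point to one unbroken gap.
- A specific row overriding the general disease progression row is how the table works elsewhere, for instance for new anticancer therapy. That conflict is weak evidence taken alone.
- In ordinary usage, an event after missed assessments, censored at the assessment before them, means the gap leading up to the event.
- Nothing shows that programming would follow the table rather than the text.

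These points stand, and they make the text the probable intention. They do not remove the difference in wording, supply a rule of precedence, or make the timing of the gap explicit.

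The size is also open to challenge. The 48-month figures are the large case; at 12 months the loss is negligible.

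A reader might also infer bias between arms because the study is open label. The documents contain nothing on scan attendance by arm, so that remains conjecture.

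**Conclusion.** The contradiction is confirmed word for word: the SAP text and the protocol require consecutive misses, the Table 3 row does not, and none of the three ties the gap to the event. Events would be lost only if the row, or to a lesser degree the text, were coded literally.

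In that case the loss runs from negligible with short follow-up to several events in 120 patients with long follow-up. The figures rest on assumed miss rates, independent misses, exponential PFS and assumed follow-up lengths, none of which the documents give. No effect on the hazard ratio or on the trial's conclusion has been calculated.

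The consequence is confined to PFS. It is a secondary endpoint, outside the Hochberg list of CR rate, DOR and TTR, without a formal test under the protocol, and possibly analysed only later. The primary ORR analysis does not use this rule. It is worth correcting because the repair is simple and belongs before database lock.

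**What to change.** Use one rule, worded identically in the SAP 6.1.2.5 sentence and the Table 3 row: *Death or PD immediately following 2 or more consecutive missed scheduled tumor assessments, with no evaluable assessment between the gap and the event: censor at the last evaluable assessment before the gap, or at the randomization date if there is none.*

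Two clarifications belong with it:

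- State whether a not-evaluable scan closes a gap and whether it can supply the censoring date. SAP 6.2 counts such scans when setting censoring dates, so the new wording must be aligned with it.
- State that this row overrides the general event rows, and that the SAP text governs if text and table still differ.

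The cost is two lines of SAP wording, these clarifications and the matching program. No new data are needed.
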